5.10 Power analyses

What effect size could we expect to find statistically significant for the whole cohort given an estimated sample size of 176 patients?

Effect size for comparison between mean Hb pre and post intervention for whole cohort (matched pairs samples t-test) of 176 patients. Assuming data are normally distributed.

Sample size = 176, power = 80%, two-tailed significance 0.05

Effect size ~ 0.21

```
pwr.t.test(n = 176, d = NULL, sig.level = 0.05, power = 0.8,
type = "paired", alternative = "two.sided")
```

Paired t test power calculation

n = 176
d = 0.2123609
sig.level = 0.05
power = 0.8
alternative = two.sided

NOTE: n is number of *pairs*

What effect size could we expect to find statistically significant for the cohort of patients with IDA given an estimated sample size of 176 anaemic patients, if the incidence of IDA is unknown?**

IDA prevalence	IDA Sample size	Effect size (matched pairs samples t-test)	Effect size (Wilcoxon signed-rank test (matched pairs))
0,2	35	~0.5	~0.5
0,3	53	~0.4	~0.4
0,4	70	~0.34	~0.35
0,5	88	~0.3	~0.31

5.11 Statistical analysis

Categorical variables will be reported as number and percentage. All patient and surgical characteristics will be compared between children with and without anaemia and comparing children with IDA versus anaemia of other cause using Pearson's chi-squared or Fisher's exact tests as appropriate. These will include age groups, sex, type of surgery (general, orthopaedic, ENT, plastics, other), severity of surgery as per SAPSOS definitions (mild, moderate, severe), severity of anaemia as per WHO definitions (mild, moderate, severe).

Normal distribution of continuous variables will be determined by Shapiro-Wilk testing and summarised appropriately as means \pm standard deviation or as medians \pm interquartile range (IQR). All patient and surgical characteristics will be assessed with parametric testing (Student's t-test) for normally distributed data, and nonparametric testing (Mann-Whitney U test or Kruskal-Wallis test) for non-normally distributed data. These data will include pre-intervention Hb, post-intervention Hb, and duration of oral iron treatment (days).

Pre- and post-intervention Hb for the patient with IDA will be assessed by a paired t-test if data are normally distributed, and if data are not normally distributed then the data will be analyse using Wilcoxon ranked sum test.

Is there a statistically significant difference in pre and post intervention Hb in the IDA patients after adjusting for baseline haemoglobin?

The proposal is to use a mixed effect regression model. The final model will depend on the distribution of the outcome variable (post-intervention Hb). If the outcome is normally distributed, a linear mixed effect model will be used. If the outcome is not normally distributed, different approaches can be used depending on how skewed the outcome is e.g. Generalised Linear Mixed Effect Model

7. Study organisation and management

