5.2 Primary outcome measure

DHb (pre-intervention Hb – post-intervention Hb)

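### A normality check picks the test for the primary Hb comparison; its two branches test different quantities, and the fallback named in section 5.11 is an unpaired test

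*Combined protocol and SAP*

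**What the plan says.** The primary outcome (section 5.2) is DHb, the within-child difference between pre- and post-intervention Hb. Three statements bear on how it is tested.

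- Section 5.11, general rule: "Normal distribution of continuous variables will be determined by Shapiro-Wilk testing". This sentence concerns description and general testing. It gives no cut-off and does not name DHb.
- Section 5.11, primary comparison: "Pre- and post-intervention Hb for the patient with IDA will be assessed by a paired t-test if data are normally distributed". The fallback branch of the same rule reads: "if data are not normally distributed then the data will be analyse using Wilcoxon ranked sum test".
- Section 5.10, Power analyses: the calculation compares mean Hb before and after treatment with a paired t-test ("Sample size = 176, power = 80%, two-tailed significance 0.05"). The table for the IDA cohort adds a column for the "Wilcoxon signed-rank test (matched pairs") version.

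Section 5.11 does not say whether normality is judged on DHb or on pre and post Hb separately. No section says whether the target is a mean or a rank-based change, and none gives an SD, skewness or shape for DHb.

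**The concern.** The primary test, and with it the quantity being tested, is unknown until the data are seen. The t-test branch addresses the mean change, which is what the study was sized on. The non-normal branch addresses something else.

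What that something is depends on how the fallback is read. The rank-sum test named in section 5.11 compares two independent samples and ignores the pairing. The signed-rank test in the power table uses the pairing, but its null is that DHb is symmetric about zero. A skewed DHb can have a mean of exactly zero and still violate that null.

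At stake is whether the single efficacy result can be read as a statement about mean Hb at the nominal 5% level, or alternatively whether the study keeps the power it claims.

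**Working it through.** **Inputs from the documents.** Two-sided 0.05 and 80% power; 35, 53, 70 or 88 IDA pairs for IDA prevalence 0.2 to 0.5 among 176 anaemic children (section 5.10, Power analyses); 44 IDA patients expected in the site table (section 6.7).

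**Assumptions, because the documents are silent.** Shape of DHb: gamma (skewness 2/√k) and lognormal (skewness (e^{σ²}+2)√(e^{σ²}−1); σ = 0.5 gives 3.284 × 0.533 = 1.75). Shapiro-Wilk cut-off: 0.05, applied to DHb. Pre/post correlation: 0.5 to 0.7.

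**Step 1: the plan's own figures.** The detectable d solves the paired-t power equation with noncentrality d√n. For n = 176, d = 0.2123 (power 0.8001 at the stated d). For n = 35, 53, 70 and 88, d = 0.488, 0.392, 0.340 and 0.302. Multiplying n by the signed-rank efficiency 0.955 gives 0.50, 0.40, 0.348 and 0.309. All agree with the power table.

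**Step 2: fallback read as signed-rank.** DHb was centred to a true mean of zero, with 8,000 simulated trials per cell. Rejection rates (%) are: rule as planned / signed-rank always / paired t-test always.

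| DHb shape (skewness) | 35 pairs | 44 pairs | 88 pairs |
|---|---|---|---|
| Normal (0) | 4.7 / 4.4 / 4.6 | 5.1 / 5.0 / 4.9 | 5.4 / 5.3 / 5.4 |
| Gamma (0.5) | 5.6 / 5.6 / 5.0 | 6.2 / 6.2 / 5.5 | 6.1 / 6.4 / 4.7 |
| Gamma (1.0) | 8.1 / 8.2 / 5.8 | 8.2 / 8.3 / 5.4 | 12.5 / 12.6 / 5.4 |
| Gamma (1.5) | 11.3 / 11.3 / 6.1 | 13.5 / 13.5 / 6.0 | 21.4 / 21.4 / 5.5 |
| Lognormal (1.75) | 12.3 / 12.5 / 6.3 | 14.1 / 14.1 / 6.1 | 22.5 / 22.6 / 5.4 |

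The Monte Carlo standard error is √(0.05 × 0.95 / 8000) = 0.24 points near 5%, and √(0.225 × 0.775 / 8000) = 0.47 points near 22.5%.

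Two things follow. The first two figures in each cell are almost equal, so the excess comes from using a rank test for a mean, not from the pre-test. And under skew the excess grows with sample size, while the t-test stays close to 5%.

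**Step 3: no effect at all.** If pre and post Hb are skewed but exchangeable (correlation 0.6, 10,000 trials), DHb is symmetric and the planned rule rejects in 4.5-5.2%.

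**Step 4: direction.** With the rise in Hb right-skewed (lognormal, σ = 0.5) and mean change zero, rejections split into 13.1% pointing to a fall and 0.3% to a rise at 44 pairs, and 22.8% and 0.05% at 88 pairs. Left skew reverses this.

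**Step 5: fallback read literally as rank-sum.** For normal data with equal variances, the effect in units of the Hb SD is d√(2(1−ρ)). The rank-sum statistic then has mean about d√n·√(1−ρ)·√0.955 and true SD about √(1−ρ), while the test assumes SD 1. So power ≈ Φ(d√n·√0.955 − 1.96/√(1−ρ)).

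At 44 pairs, d = 0.432 and d√n·√0.955 = 0.432 × 6.633 × 0.977 = 2.80:

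- ρ = 0.5: Φ(2.80 − 2.77) = 51%
- ρ = 0.6: Φ(2.80 − 3.10) = 38%
- ρ = 0.7: Φ(2.80 − 3.58) = 22%

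Simulation at 35, 44 and 88 pairs gives about 50%, 35-40% and 21-24%, against about 80% for the paired t-test. Under the exchangeable null with skewed Hb and ρ = 0.6, rank-sum rejected in only 0.2-2.0%.

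**The case against.** The best defence is that choosing between a t-test and a Wilcoxon test on normality is familiar practice, that rank-sum is probably a slip for signed-rank, and that a true absence of effect gives a symmetric DHb and a 5% error rate. All of that is fair as far as it goes. Step 3 confirms the last part.

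A reader might go further and infer that the Shapiro-Wilk pre-test itself inflates the false-positive rate of this trial to 13-23%. The documents do not support that:

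- They give no shape for DHb, and the power section assumes normality. Rates of that size need skewness of about 1.4 to 1.75, which is strong; at 0.5 to 1.0 the range is about 6-12%.
- The upper end needs 88 pairs, the most favourable row of the power table. The site table expects 44.
- Always using signed-rank gives the same rates, so the pre-test is only the route into the rank branch.
- The general Shapiro-Wilk sentence does not name DHb and gives no cut-off, so any simulation of the rule fills in details the plan leaves out.

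A reader might also take this to mean false claims of benefit. Step 4 shows that the direction follows the direction of skew, which is unknown. With a few strong responders, nearly all the false results would point to a fall in Hb.

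What stands is that exchangeability is a narrower condition than no mean change. In an uncontrolled pre-post study, a minority responding while others fall slightly would give a skewed DHb with zero mean. The undefined target and the rank-sum/signed-rank conflict need no assumed shape at all.

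**Conclusion.** The point holds as a defect of specification. Section 5.11 lets the data choose between two tests of different quantities for the primary outcome, while the study is sized on the mean. It also names an unpaired fallback that conflicts with section 5.10.

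The consequences are conditional:

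- **Signed-rank intended.** The error rate for a mean change at 35-88 pairs is about 5% with symmetric DHb, about 6-12% at skewness 0.5-1.0 and about 11-23% at 1.4-1.75, against about 5-6.5% for a fixed paired t-test. These rest on assumed gamma and lognormal shapes, a mean change of exactly zero and a 0.05 cut-off for the normality check.
- **Rank-sum used as written.** Type I error is not inflated in the exchangeable case, but power at the plan's detectable effects drops from about 80% to about 50%, 35-40% and 23% at correlations 0.5, 0.6 and 0.7. This rests on normal data and those assumed correlations.

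On either reading, the switch gives no protection that the paired t-test needs at the planned sizes for skewness up to about 1.75.

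**What to change.** In section 5.11, remove the normality switch for the primary outcome. State that the primary analysis is mean DHb with its 95% CI and a paired t-test, whatever the distribution. Name a bootstrap CI for the mean and the Wilcoxon signed-rank test (not rank-sum) as sensitivity analyses, and use plots of DHb for description only. Add a sentence on how the baseline-adjusted mixed model relates to this analysis, since its form is also left to the distribution of post-intervention Hb.

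The cost is SAP wording only; sample size and data collection do not change. The downside is some loss of efficiency if DHb turns out symmetric with heavy tails, a case that the signed-rank sensitivity analysis would show.

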6.7 Recruitment and screening

Eligible subjects will be identified at routine surgical outpatient appointments. Paper informed consent will be obtained prior to a finger-prick screening haemoglobin (Hemacue) is performed, with translators where necessary, from the primary parent or legal guardian or legally authorised representative and included assent of the child where appropriate. Broadcasting through an appropriate hospital notice will inform the patients, their parents/guardians and the public that the hospital is participating in the study (Appendix C).

The total patients planned to be recruited for screening is 1110 patients and these will be divided across 7 sites:

Sites		Number of patients to be screened	Estimated number of patients with IDA
Western Cape		460	18
Red Cross War Memorial Children's Hospital		310	12
Tygerberg Hospital		150	6
KwaZulu-Natal		250	10
Inkosi Albert Luthlui Hospital		150	6
Greys Hospital		100	4
Gauteng		400	16
Steve Biko Hospital		100	4
Kalafong Hospital		100	4
Chris Hani Baragwanath Hospital		100	4
Charlotte Maxeke Johannesburg Academic Hospital		100	4
Total		1110	44

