5.10 Sample size calculation

How many patients will need to have a screening finger-prick Hb for the pilot study to be a representative of children undergoing noncardiac surgery with preoperative anaemia?

Secondary analysis of SAPSOS study found 46.2% patients were anaemic, using estimation for a single proportion with a specified precision and allowing for 10% drop out.

$$n = [p(1-p)z^2] / d^2$$

n: sample size

p: population proportion

z: 1.96, level of confidence, normal distribution

d: 0.05, acceptable margin of error

$$n = 0.46.(0.538)3.8416 / 0.0025 = 381.98$$

10% drop out rate: 38.2

Sample size: $382 + 38 = 420$

Given a sample size of 420 patients allowing for 10% drop-out approximately how many anaemic patients will be enrolled?

$$n = 420 * 0.90 * 0.462 \sim 176$$

[figure not shown]

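### Minor, free improvement: name Welch's t-test in section 5.11, because the IDA versus other-anaemia groups are likely to be very unequal in size and a moderate difference in SD would shift the pooled test's error rate

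*Combined protocol and SAP*

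**What the plan says.** Section 5.11 tests continuous variables for normality with Shapiro-Wilk. For those that pass, "All patient and surgical characteristics will be assessed with parametric testing (Student's t-test) for normally distributed data". The rest go to "nonparametric testing (Mann-Whitney U test or Kruskal-Wallis test) for non-normally distributed data". Equality of variances is neither assumed in words nor checked, and no unequal-variance version of the test is named.

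The t-test sentence names no groups. The contrasts appear in the preceding paragraph on categorical variables: children with and without anaemia, and "comparing children with IDA versus anaemia of other cause using Pearson's chi-squared or Fisher's exact tests as appropriate". Both paragraphs speak of all patient and surgical characteristics, so the natural reading is that the same two contrasts apply to continuous variables.

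The expected group sizes come from three places:

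- Section 6.7: "The total patients planned to be recruited for screening is 1110 patients", with a site-table column headed "Estimated number of patients with IDA" that totals 44.
- Section 5.10 Sample size calculation: "Secondary analysis of SAPSOS study found 46.2% patients were anaemic".
- Section 5.10 Power analyses works on a different base, "given an estimated sample size of 176 anaemic patients, if the incidence of IDA is unknown", and tabulates 35, 53, 70 and 88 children with IDA.

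**The concern.** Student's t-test estimates one common variance. When one group is much larger, that estimate is essentially the larger group's variance, whereas the uncertainty of the mean difference comes mainly from the smaller group. If the small IDA group is the more variable, the standard error is too small and false positives rise. If it is the less variable, the standard error is too large and real differences are missed. A normality check does not detect this.

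At stake are the p-values on how children with IDA differ from other anaemic children, for example in pre-intervention Hb, age or weight. They could carry an error rate other than the nominal 5%, in a direction that the reader of the report could not see.

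**Working it through.** **Group sizes.** Anaemic children: 1110 × 0.462 = 512.8, about 513. Without IDA: 513 − 44 = 469, a ratio of 1 : 10.7. Taking 10% drop-out off the anaemic total, 513 × 0.9 = 462 and 462 − 44 = 418. From the power table: 176 − 35 = 141, 176 − 53 = 123, 176 − 70 = 106, 176 − 88 = 88.

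**The plan's own figures.** The documents state no figure for a two-group t-test. Their other calculations reproduce: a paired t-test with 176 pairs, 80% power and two-sided 0.05 detects d = 0.2123 (stated 0.2123609), and the table rows come to 0.49, 0.39, 0.34 and 0.30 (stated ~0.5, ~0.4, ~0.34, ~0.3).

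**Formula.** Let r = SD(IDA)/SD(other), with SD(other) = 1 and equal means.

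- True variance of the mean difference: V = r²/n₁ + 1/n₂
- Variance the pooled test uses, on average: P = {[(n₁ − 1)r² + (n₂ − 1)]/(n₁ + n₂ − 2)} × (1/n₁ + 1/n₂)
- Approximate false-positive rate: 2 × Pr(Z > t × √(P/V)), with t = 1.9646 on 511 degrees of freedom at 44 v 469

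**Worked at 44 v 469.**

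- r = 1.5: V = 0.05327, P = 1.1052 × 0.02486 = 0.02747, √(P/V) = 0.718, effective cut-off 1.411, rate 15.8%.
- r = 1.25: V = 0.03764, P = 0.02604, √(P/V) = 0.832, cut-off 1.634, rate 10.2%.
- r = 0.67: V = 0.01233, P = 0.02371, √(P/V) = 1.386, cut-off 2.724, rate 0.65%.

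**More exact rates.** The approximation ignores sampling error in the variances. Averaging the normal tail probability over 2,000,000 simulated chi-square variances, for normal data, gives these false-positive rates for the pooled test (%):

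| IDA v other | r = 0.67 | 0.8 | 0.95 | 1.05 | 1.25 | 1.5 |
|---|---|---|---|---|---|---|
| 44 v 469 | 0.67 | 1.86 | 4.09 | 5.98 | 10.29 | 15.89 |
| 35 v 141 | 1.36 | 2.54 | 4.33 | 5.70 | 8.61 | 12.18 |
| 53 v 123 | 2.27 | 3.26 | 4.55 | 5.45 | 7.25 | 9.31 |
| 70 v 106 | 3.44 | 4.05 | 4.77 | 5.23 | 6.10 | 7.03 |
| 88 v 88 | 5.02 | 5.01 | 5.00 | 5.00 | 5.01 | 5.02 |

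With 418 in place of 469, ratios 1.25 and 1.5 give 10.1% and 15.6%. Welch's test stays at 5.0% in every cell.

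**The other contrast.** Anaemic v non-anaemic is 513 v 1110 − 513 = 597. Here the pooled test stays between 4.0% and 6.1% for ratios from 0.5 to 2.

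**Which variables are reached.** Section 5.11 names pre-intervention Hb, post-intervention Hb and days of iron. Section 6.13 lists the last two only for patients with IDA, so they cannot be compared with other anaemic children. That leaves pre-intervention Hb and characteristics recorded in both groups, such as age and weight.

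**The case against.** A reader might infer that any difference in spread takes the test far from 5%. The documents do not support that: they give no SD for either group, and at 44 v 469 a ratio between 0.95 and 1.05 gives only 4.1% to 6.0%. Nor do they fix 44 v 469 as the split. It means 44/513 = 8.6% IDA among anaemic children, while the power table assumes 20% to 50%, and the distortion shrinks along that range until it vanishes at 88 v 88. Both limits stand.

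It can also be said that the normality check would send the affected variables elsewhere. Age is bounded, and Hb is selected by an anaemia cut-off. In a simulation under assumed shapes (uniform age, Hb truncated by a noisy screening test), Shapiro-Wilk rejected in nearly every run at n = 469 (100% and 99.8%) and in 100% and 70% at n = 141. The shapes are assumptions, but the point stands in part: the rates above apply only to variables that reach the t-test. The fallback is not immune either. At 44 v 469 with equal means and medians, Mann-Whitney rejected in 9.5% of simulated data sets at ratio 1.5 and 1.6% at 0.67.

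Finally, Student's t-test is sometimes used as a generic name, and the plan never states that variances will be pooled. That is true. The pooled test is what the name ordinarily means, and one word removes the doubt.

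**Conclusion.** The point holds as a minor one. If IDA and other anaemia are compared with the pooled test at about 44 v 469, moderate SD differences (assumed ratios 1.25 to 1.5) give about 10% to 16% false positives, and ratios of 0.67 to 0.8 give about 0.7% to 1.9%. At ratio 1.5 the rate is 12.2% at 35 v 141, 7.0% at 70 v 106 and 5.0% at 88 v 88. These figures assume normal data and equal means. The true SD ratio is unknown.

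A reader might take this as a threat to the trial's conclusions. It is not. The primary outcome is the within-patient change in Hb, analysed by a paired test, and the only secondary outcome, IDA incidence, is a proportion. Neither uses the two-group t-test. What is affected is the descriptive comparison of IDA with other anaemia, and the anaemic v non-anaemic contrast is barely touched.

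**What to change.** In section 5.11, replace Student's t-test with Welch's unequal-variance t-test for unpaired two-group comparisons of continuous variables, and report each mean difference with its Welch 95% CI. The strongest reason is the IDA v other-anaemia contrast; using the same test for the near-balanced contrast is for consistency.

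The cost is one phrase in the plan. No extra data or patients are needed, and when the variances are equal both tests have a 5.0% false-positive rate at 44 v 469.

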Exclusion criteria	Patient or parent refusal Surgery planned in not less than 4 weeks from surgical outpatient visit Known history of acquired iron overload, family history of haemochromatosis or thalassemia Known reason for anaemia (e.g. untreated vitamin B ₁₂ or folate deficiency or haemoglobinopathy) Treatment with oral iron, erythropoietin, IV iron therapy or blood transfusion in the previous 12 weeks Known hypersensitivity to oral iron or other contraindication to oral iron Temperature > 38.0 °C or receiving non-prophylactic antibiotics
Statistical analysis	The primary outcome measure is comparison of pre-intervention and post-intervention haemoglobin
Proposed start date	08 February 2023
Proposed end date	26 July 2024
Trial duration	Recruitment in outpatient clinic and follow-up until day of surgery

3. Introduction

Studies in both paediatric and adult patients have shown an association between preoperative anaemia and increased postoperative morbidity and mortality, and transfusion rates²⁻⁷. The incidence of preoperative anaemia in the secondary analysis of the SAPSOS cohort of children who underwent noncardiac surgery was 46.2%⁴. Iron deficiency anaemia (IDA) has been shown to represent up to 30% of preoperative anaemia in adults⁸. Iron deficiency and IDA are of even greater concern in children, because of the negative impact it may have on cognitive performance⁹.

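### The non-normal fallback for the paired Hb comparison is named as an independent-samples test, and the plan does not say that normality is judged on DHb

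*Combined protocol and SAP*

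**What the plan says.** The primary outcome is a within-child change: section 5.2 (Primary outcome measure) gives it as "DHb (pre-intervention Hb – post-intervention Hb"), and section 2 (Summary) says "The primary outcome measure is comparison of pre-intervention and post-intervention haemoglobin".

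For the test, section 5.11 (Statistical analysis) states: "Pre- and post-intervention Hb for the patient with IDA will be assessed by a paired t-test if data are normally distributed". The same sentence continues: "if data are not normally distributed then the data will be analyse using Wilcoxon ranked sum test".

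Section 5.10 (Power analyses) tabulates detectable effects for the iron-deficient children under two tests, a matched-pairs t-test and the "Wilcoxon signed-rank test (matched pairs").

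On the distribution check, section 5.11 says "Normal distribution of continuous variables will be determined by Shapiro-Wilk testing". It then sets a rule for choosing between Student's t-test and the "Mann-Whitney U test or Kruskal-Wallis test" for patient and surgical characteristics, and lists pre-intervention Hb, post-intervention Hb and treatment duration among the data concerned. DHb is not named there, nor in the sentence on the paired comparison.

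**The concern.** Two sections of one plan name different tests for the same comparison. The rank-sum test treats the pre and post values as coming from unrelated children, while the power table relies on the pairing. An analyst following section 5.11 to the letter would give up the pairing whenever the fallback was used.

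How often that happens depends on what is tested for normality. The paired t-test needs roughly normal differences, so DHb is the relevant variable. Children enter only if their screening Hb is below a WHO cut-off, which cuts off the upper part of the pre-intervention Hb distribution. A Shapiro-Wilk test on raw Hb can therefore reject even where DHb is normal. At stake is the power to show a modest rise in Hb and, if the data are skewed, what the fallback's p-value means.

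**Working it through.** **1. The plan's own figures.** For a paired t-test with n pairs, power at two-sided 0.05 is approximately P(T > t(0.975, n−1)), with T noncentral t on n−1 degrees of freedom and noncentrality d√n. Solving for 80% power at n = 176 gives d = 0.2124 (section 5.10: 0.2123609). For the signed-rank test with normal differences, n is replaced by n × 3/π.

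| n | paired t: recomputed | stated | signed-rank: recomputed | stated |
|---|---|---|---|---|
| 35 | 0.487 | ~0.5 | 0.500 | ~0.5 |
| 53 | 0.392 | ~0.4 | 0.402 | ~0.4 |
| 70 | 0.340 | ~0.34 | 0.348 | ~0.35 |
| 88 | 0.302 | ~0.3 | 0.309 | ~0.31 |

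The power table is sound, and its second column is a signed-rank calculation. The discrepancy lies in section 5.11.

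**2. Why the name matters.** With equal SDs σ and correlation ρ among the analysed children, the variance of the change is 2σ²(1−ρ), but an unpaired test assumes 2σ². Its statistic is therefore roughly √(1−ρ) times the paired one. At ρ = 0.5 the factor is √0.5 = 0.71, so a paired statistic of about 1.96/0.71 = 2.8 is needed for significance.

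**3. Inputs for the two-stage rule.** n = 44 is the total in the column "Estimated number of patients with IDA" of section 6.7. The value d = 0.45 lies between the 0.5 at n = 35 and the 0.4 at n = 53 in section 5.10. The lowest 46.2% on screening Hb are selected, matching the anaemia proportion in section 3. The following are assumptions: bivariate normal Hb, one cut-off rather than age-specific ones, disagreement of 0 to 0.5 SD between finger-prick and laboratory Hb, and a population pre-post correlation of 0.4, 0.6 or 0.8. After selection, the correlation among the analysed children is 0.25–0.29, 0.40–0.46 and 0.62–0.68 respectively.

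**4. Results of simulating the rule.** Each simulated trial uses the paired t-test unless Shapiro-Wilk rejects, and then the rank-sum test. Raw Hb counts as rejected if either the pre or the post values fail.

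| Variable checked | Fallback used | Power at 0.4 | at 0.6 | at 0.8 |
|---|---|---|---|---|
| DHb | 4–6% of trials | 81–84% | 81–84% | 81–84% |
| Raw pre/post Hb | about 21–91% | 69–79% | 61–78% | 44–71% |
| None (paired t always) | – | 82–86% | 82–86% | 82–86% |

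The DHb and paired-t ranges are pooled over the three correlations. The exact power of the paired t-test is 83.1%, so the spread in the last row reflects simulation error.

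The raw-Hb trigger comes mainly from truncation. Pre-intervention Hb alone fails Shapiro-Wilk in about 90%, 42% and 16–18% of samples at 0, 0.3 and 0.5 SD screening disagreement, against 5–6% for DHb. As a rough check of the worst case (zero disagreement, correlation 0.8), rank-sum power is about 39% and paired-t power about 83%, so 0.91 × 39% + 0.09 × 83% ≈ 43%. This agrees with the simulated 44%.

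**5. Skewed data.** With exponential post-Hb residuals (an assumption; 0.3 SD screening disagreement) and zero mean change, the rank-sum test rejected in about 17% of trials at correlation 0.4 and 9–10% at 0.6. The signed-rank test rejected in 15–19% over 0.4–0.8, because it assumes symmetric differences.

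**The case against.** The strongest reply is that this is one wrong word whose meaning can be recovered. The sentence opens with a paired t-test, the unpaired rank test has its own name elsewhere in section 5.11, and section 5.10 names the matched-pairs test. That stands: a reader might infer an intention to discard the pairing, and the documents do not support it. It is a reason to rate the point low. It does not make the named test correct.

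A reader might also take the power of the rank-sum test applied in every trial as the plan's power: 69–70%, 56–60% and 30–39% at correlations 0.4, 0.6 and 0.8 with the inputs above. That overstates the loss, since the rank-sum test is used only after normality is rejected. If DHb is checked, power is nearly unaffected.

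Thirdly, a paired t-test conventionally implies a check on the differences, so leaving DHb unnamed may be harmless. This stands in part. Section 5.11 does not say that raw Hb decides the paired comparison; its list of Hb variables belongs to the rule for patient and surgical characteristics. But that list is the nearest guidance an analyst has, and it points to raw Hb.

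The mixed-model analysis later in section 5.11 does not settle the matter, because it is a proposal with its final form left open.

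**Conclusion.** The point holds as a minor one. The fallback named in section 5.11 is wrong for paired data and contradicts section 5.10, and the variable on which normality is judged is not stated. Section 5.10 needs no correction.

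Under the assumed normal data the cost is at most a few percentage points of power if DHb is checked. If raw Hb is checked it ranges from a few points to about half the power, with the worst case at correlation 0.8 and no screening disagreement. The documents give neither the correlation nor the screening disagreement, so these are ranges over assumed values and not estimates for this trial.

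A reader might infer that the slip can only make the test conservative. With normal data and clearly positive correlation it does, but the fallback is meant for non-normal data, and in the skewed example the rank-sum test exceeded 5% for zero mean change. The signed-rank test did so too. It is the right paired counterpart and matches the power table, but with skewed DHb it should not be read as a test of mean change.

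**What to change.** In section 5.11, replace the rank-sum test with the Wilcoxon signed-rank test as the fallback for pre- versus post-intervention Hb, so that it agrees with section 5.10. In the same sentence, state that normality for this comparison is assessed on DHb.

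The signed-rank test has 81–82% power in the same normal settings, so correcting the name removes nearly all of the loss. Naming DHb ties the choice of test to the assumption that the paired t-test makes.

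The cost is two phrases of SAP wording. No new data, patients or procedures are needed, and the sample size is unchanged.
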